12. STATISTICAL METHODS AND SAMPLE SIZE DETERMINATION BY ASTRAZENECA

12.1 Description of analysis sets

The evaluation of efficacy will be performed for the full analysis set as outlined below. The primary efficacy variable and selected secondary variables may be reanalyzed using the per-protocol analysis set if more than 10% of the patients in any treatment group in the full analysis set are excluded from the per-protocol analysis set.

The primary analysis will be based on the full analysis set using the last observation carried forward approach (LOCF).

The analysis of safety will be based on the safety analysis set.

A detailed description of analysis sets is given below. The decision to include or exclude patients from each analysis set will be based on relevant protocol deviations and will be performed in a blind data review prior to unblinding. A summary of the number of patients per analysis set will be given and reasons for exclusion of patients from an analysis set will be listed.

12.1.1 Full analysis set

The full analysis set will include all randomised patients (as randomised) who received at least one dose of study medication during the 24-week double-blind short-term treatment period who have a non-missing baseline value and at least one post-baseline value for at least one efficacy variable to be analyzed at week 24. The intention-to-treat principle will be preserved despite the exclusion of patients who took no study medication, as the decision of whether or not to begin treatment during the randomised treatment period could not be influenced by knowledge of the assigned treatment. Where appropriate, missing data will be replaced using the last observation carried forward (LOCF) approach.

12.1.2 Per-protocol analysis set

The per-protocol analysis set is a subset of the full analysis set consisting of patients who do not violate the terms of the protocol, which may affect the primary efficacy endpoint significantly. All decisions to exclude patients from the full analysis set to create the per-protocol analysis set will be made prior to the unblinding of the study.

12.1.3 Safety analysis set

The safety analysis set will include all randomised patients who received at least one dose of study medication and who provide any safety records. Patients who were dispensed the wrong randomised treatment (ie those randomised to dapagliflozin 10 mg but actually given placebo, or vice versa) for the duration of the first 24 weeks will be counted in the treatment group for which they received medication. Where appropriate, missing data will be replaced using the last observation carried forward (LOCF) approach.

12.2 Methods of statistical analyses

12.2.1 Analysis of the 24-week double-blind short-term treatment period

The primary objective of this study is to show superiority of dapagliflozin versus placebo in terms of the primary efficacy variable change in HbA1c from baseline to week 24.

The following null hypothesis H_0 will be tested against the alternative hypothesis H_A ($\alpha=0.050$, two-sided):

$$H_0: \mu_T - \mu_P = 0,$$

$$H_A: \mu_T - \mu_P \neq 0,$$

where μ_T denotes the mean absolute change in HbA1c from baseline to week 24 in the group of patients treated with dapagliflozin as add-on therapy to on a combination of a sulfonylurea and metformin (test medication, T) and μ_P the mean absolute change in HbA1c from baseline to week 24 in the group of patients treated with placebo as add-on therapy to a combination of a sulfonylurea and metformin (placebo, P).

Four key secondary variables have been identified:

- Change in fasting plasma glucose (FPG) from baseline to 24 weeks.
- Change in total body weight from baseline to week 24.
- Proportion of patients achieving a therapeutic glycaemic response, defined as HbA1c <7.0%, 24 weeks.
- Change in seated systolic blood pressure (SBP) from baseline to week 8.

A hierarchical closed testing procedure will be used to control the Type I error rate across the primary and key secondary objectives. If the primary endpoint is statistically significant, key secondary variables will be tested in the order presented within this protocol. Treatment comparisons will be individually tested at a two-sided significance level of 0.050. For all other variables, nominal p-values will be reported without significance testing.

Other secondary efficacy variables and safety variables shall provide supportive efficacy and safety information regarding the differences between the treatment groups.

The primary and secondary efficacy analyses will be based on the full analysis set. The primary efficacy variable and selected secondary variables may be reanalyzed using the per-protocol analysis set if more than 10% of the patients in any treatment group in the full analysis set are excluded from the per-protocol analysis set.

The LOCF approach means that for all changes (or percent changes) from baseline to a specific time point post-baseline, analyses will be based on measurements available at that time point or the last post-baseline measurement prior to the time point, if no measurement is

available at that time point. Unless otherwise specified, if a patient initiates rescue medication, the last value taken on or before the first rescue dose will be used for analysis.

The primary efficacy variable, change in HbA1c from baseline to week 24, will be analyzed by an analysis of covariance (ANCOVA) model including terms for treatment group and baseline covariate. The ANCOVA model will be used to derive a least squares estimate of the treatment difference with 95% confidence interval and corresponding two-sided p-value. Further, two-sided 95% confidence intervals for the mean change within each treatment group will be calculated. The same method will be applied for analyzing other continuous efficacy variables.

The proportion of patients achieving a therapeutic glycaemic response, defined as HbA1c <7.0%, at week 24, will be analyzed using the methodology of Zhang, Tsiatis and Davidian and Tsiatis, Davidian, Zhang and Lu when there are at least 5 responders on average by treatment group. For proportion of responders, estimates, confidence intervals, and tests will be obtained using this methodology with adjustment for baseline HbA1c. For each treatment group, the probability of response is first modeled using a logistic regression model with baseline HbA1c as a term. Treatment group estimates of response rate are then obtained by integrating each group's modeled probability of response over the observed distribution of baseline covariate). The difference in response rate between dapagliflozin and placebo will be displayed along with the 95% confidence intervals. P-values will be calculated (when applicable). When there are less than 5 responders on average by treatment group, the unadjusted proportions and difference between unadjusted proportions, exact 95% confidence interval, and p-values from the Fisher's exact test (when applicable) will be provided. The same method will be applied for analyzing other proportions of patients achieving a pre-defined response.

Other discrete variables will be summarized by counts, proportions, and corresponding two-sided 95% confidence intervals for each treatment group. Comparisons between treatments will be performed using two-sided Fisher's exact test (when applicable).

The time course of continuous variables will be presented using standard descriptive summary statistics calculated at each scheduled measuring time point and the last individual measuring time point. Moreover, standard descriptive summary statistics will be calculated for the change (absolute or percent) from baseline to each scheduled measuring time point after baseline and the last individual measuring time point.

Due to the large number of centres and the expected low number of patients per centre it will not be appropriate to explore centre effects. Tables by region will be provided in order to explore regional effects. Regional effects will be included in the statistical model in additional exploratory analyses if appropriate. Any pooling of regions with few patients in geographical clusters will be specified in the Statistical Analysis Plan (SAP) before breaking the blind.

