Week	-11	-9	-8	-2	0	4	8	16	24	32	40	52	55	
Visit window (days) ^{a)}		(0) ^{b)}	(±3)	(±3)	(±3)	(±3)	(±3)	(±7)	(±7)	(±7)	(±7)	(±7)	(+7)	
Screening informed consent and blood sample for HbA1c	X													
Informed consent		X												
Demography and medical history		X												
Inclusion / Exclusion criteria		X	X ^{d)}	X ^{d)}	X									
Randomisation					X									
Brief physical examination			X			X	X	X		X	X			
Complete physical examination		X			X				X			X	X	X

	Screening S	Enrolment 1	24-week double-blind treatment period							28-week site- and patient-blinded extension period			Follow-up 12 FU	Rescue R
Visit			2	3	4	5	6	7	8	9	10	11 ^{e)}		
Week	-11	-9	-8	-2	0	4	8	16	24	32	40	52	55	
Vital signs (BP, pulse)		X	X	X	X	X	X	X	X	X	X	X	X	X
Orthostatic BP, pulse					X	X	X	X	X			X	X	X
Weight		X	X	X	X	X	X	X	X	X	X	X	X	X
Height		X												
Waist circumference		X			X				X			X		X
12-lead ECG		X			X				X			X	X	X
Concomitant medication		X	X	X	X	X	X	X	X	X	X	X	X	X
Laboratory assessments ^{e)}		X	X	X	X	X	X	X	X	X	X	X	X	X
Pregnancy test ^{f)}		X	X	X	X	X	X	X	X	X	X	X	X	X
SAEs		X	X	X	X	X	X	X	X	X	X	X	X	X
AEs				X	X	X	X	X	X	X	X	X	X	X
Dispense investigational product via IWRS/IVRS			X		X	X	X	X	X	X	X			

	Screening S	Enrolment 1	24-week double-blind treatment period							28-week site- and patient-blinded extension period			Follow-up 12 FU	Rescue R
Visit			2	3	4	5	6	7	8	9	10	11 ^{e)}		
Week	-11	-9	-8	-2	0	4	8	16	24	32	40	52	55	
Drug accountability				X	X	X	X	X	X	X	X	X		
Diet and lifestyle advice		X	X	X	X	X	X	X	X	X	X	X	X	X
Dispense glucometer and/or supplies; provide instructions			X	X	X	X	X	X	X	X	X			X
Dispense patient diary			X	X	X	X	X	X	X	X	X			X
Patient diary review for glucometer values/ hypoglycaemic events ^{g)}				X	X	X	X	X	X	X	X			X
PRO - EQ-5D-3L					X				X			X		
PRO-SHIELD-WQ-9					X ⁱ⁾				X			X		
PRO IWQOL-Lite					X				X			X		

	Screening S	Enrolment 1	24-week double-blind treatment period							28-week site- and patient-blinded extension period		Follow-up 12 FU	Rescue R
Visit			2	3	4	5	6	7	8	9	10		
Week	-11	-9	-8	-2	0	4	8	16	24	32	40	52	55
PRO - DTSQs					X				X			X	
PRO - DTSQc												X ^{j)}	
Informed consent, blood sample for genetics ^{h)}					(X)	(X)	(X)	(X)	(X)				

^{a)} Once a patient is randomised, all visits should be scheduled relative to Visit 4. Any slippage in time from one visit must not accumulate to affect other visits.

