4.2 Exclusion criteria

Patients should not enter the study if any of the following exclusion criteria are fulfilled.

The following criteria apply to the enrolment, placebo lead-in and randomisation visits (Visits 1, 2, 3, and 4).

Endocrine and metabolic disorders

1. Diagnosis of Type 1 diabetes mellitus, known diagnosis of MODY or secondary diabetes mellitus.
2. History of diabetic ketoacidosis.
3. Symptoms of poorly controlled diabetes including, but not limited to, marked polyuria, polydipsia, and/or greater than 10% weight loss during the 3 months prior to enrolment.

4. FPG >270 mg/dL (>15 mmol/L) – assessed based on laboratory results from Visits 1, 2 and 3.
5. BMI >45 kg/m²
6. History of bariatric surgery (ie, any surgery to treat obesity; for example, gastric banding or procedures that involve bypassing or transposing sections of the small intestine). History of liposuction is allowed.
7. Diabetes insipidus.
8. Thyroid-stimulating hormone (TSH) and free T4 values outside normal range; an abnormal TSH value needs to be followed up with a free T4 test. Patients with abnormal free T4 values will be excluded.

Cardiovascular disorders

9. Recent Cardiovascular Events in a patient:
 - Acute Coronary Syndrome (ACS) within 2 months prior to enrolment.
 - Hospitalization for unstable angina or acute myocardial infarction within 2 months prior to enrolment.
 - Acute Stroke or TIA within 2 months prior to enrolment.
 - Less than 2 months post coronary artery revascularization prior to enrolment.
10. Congestive heart failure defined as New York Heart Association (NYHA) class IV, unstable or acute congestive heart failure. Note: eligible patients with congestive heart failure, especially those who are on diuretic therapy, should have careful monitoring of their volume status throughout the study.
11. Blood pressure:
 - At enrolment (Visit 1):
Systolic BP \geq 170 mmHg and/or diastolic BP \geq 110 mmHg.
 - At randomisation (Visit 4):
Systolic BP \geq 160 mmHg and/or diastolic BP \geq 100 mmHg.

Kidney or urological disorders

12. Measured serum creatinine value of \geq 1.5 mg/dL (133 μ mol/L) for male patients and \geq 1.4 mg/dL (124 μ mol/L) for female patients or renal function that would preclude treatment with metformin according to local guidance.
13. History of unstable or rapidly progressing renal disease.

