11.1.1 Change and percent change from baseline

Change from baseline will be calculated as absolute difference between the value measured at or derived for a specific time point after baseline minus baseline value. Baseline is defined as the last value collected on/or prior to Visit 4 (randomisation).

Percent change from baseline will be computed as $100 * (\text{value measured at or derived for a specific time point after baseline} - \text{baseline value}) / \text{baseline value}$.

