12.3 Determination of sample size

The sample size for this study was selected to demonstrate a difference in the mean change in HbA1c from baseline to week 24 between dapagliflozin and placebo in patients on a combination of metformin and sulfonylurea.

To detect a difference of 0.5% between dapagliflozin versus placebo for change in HbA1c from baseline to week 24, assuming a standard deviation (SD) = 1.1%, 103 evaluable patients (full analysis set) for each treatment group would provide 90% power at a significance level = 0.050. Assuming that 5% of the patients will not be evaluable in the full analysis set, 108 patients per treatment group (216 patients total) are planned for randomisation.

In 6-month dapagliflozin studies, a SD of 1.1% was selected based upon the Phase II dapagliflozin study as well as historical data from other diabetes programs.

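### Free improvement, not an error: the FPG week-24 and SBP week-8 ANCOVAs adjust for one visit's baseline, although Visit 2 and Visit 3 values are already collected

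*Protocol*

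**What the plan says.** The primary model in protocol Section 12.2.1 is an "analysis of covariance (ANCOVA) model including terms for treatment group and baseline covariate". The same section extends it: "The same method will be applied for analyzing other continuous efficacy variables". That covers FPG at week 24 and seated SBP at week 8, the first and last of the four key secondary variables. Section 11.1.1 fixes the covariate: "Baseline is defined as the last value collected on/or prior to Visit 4 (randomisation"). It is therefore one visit's value.

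Earlier values exist. In Table 3 the row "Vital signs (BP, pulse") is marked at Visits 1, 2, 3 and 4 (weeks -9, -8, -2 and 0). Table 7 schedules FPG at the same four visits, and exclusion criterion 4 in Section 4.2 already uses FPG "assessed based on laboratory results from Visits 1, 2 and 3".

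Two further facts bear on SBP. Section 6.4.8.1 makes each visit's value the average of three seated readings. Section 3.1.3 has antihypertensive medication adjusted during the lead-in for patients at or above 160 mmHg systolic or 100 mmHg diastolic.

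On power, Section 12.3 gives figures for HbA1c only.

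**The concern.** A patient's SBP or FPG on one day measures that patient's usual level with error. ANCOVA gains precision in proportion to how well the covariate predicts the outcome, and two or three visits predict better than one whenever there is visit-to-visit noise. The Visit 2 and Visit 3 values precede randomisation, so using them cannot bias the treatment comparison.

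What is at stake is the width of two confidence intervals and the power of two confirmatory tests, whose sample size was set for another endpoint. The tests run in a fixed sequence: "Treatment comparisons will be individually tested at a two-sided significance level of 0.050". FPG comes directly after the primary, so a miss there stops all later confirmatory testing. SBP comes last, so more precision there helps only the SBP test itself.

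**Working it through.** **1. The plan's own figure.** Section 12.3 targets an HbA1c difference of 0.5 percentage points at two-sided 0.05 and states its other inputs as follows: "assuming a standard deviation (SD) = 1.1%, 103 evaluable patients (full analysis set) for each treatment group would provide 90% power". Power is Φ(0.5 / (1.1 × √(2/103)) − 1.96) = 90.4% by the normal approximation and 90.1% by the t-test. The t-test solution is 102.7, that is 103 per arm. The figure reproduces and nothing below changes it. No SD, effect, correlation or power is given for SBP or FPG, so every correlation from here on is an assumption.

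**2. Formula.** As a fraction of outcome variance, ANCOVA leaves 1 − c′S⁻¹c, where S is the covariance of the covariates and c their covariance with the outcome. With one baseline this is 1 − ρ². With k visits at equal correlation ρ it is 1 − kρ²/(1 + (k−1)ρ).

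**3. Equal correlation (the favourable case).** Visit 4 alone against Visits 2, 3 and 4:
- ρ = 0.5: 0.750 to 0.625, a cut of 17%
- ρ = 0.6: 0.640 to 0.509, a cut of 20%
- ρ = 0.7: 0.510 to 0.388, a cut of 24%

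With Visit 3 alone added, the cuts are 11%, 14% and 17%. In this case SBP and FPG gain equally.

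**4. Correlation partly fading, SBP at week 8.** Let the correlation between visits s weeks apart be p + d·exp(−s/20), with p the stable share of variance, d = 0.2 the fading share and the rest visit noise.

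| p | Visit 4 to week 8 correlation | Visit 4 only | plus mean of Visits 2 and 3 | plus Visit 3 only |
|---|---|---|---|---|
| 0.40 | 0.534 | 0.715 | 0.622 (cut 13%) | 0.648 (cut 9%) |
| 0.45 | 0.584 | 0.659 | 0.565 (cut 14%) | 0.591 (cut 10%) |
| 0.55 | 0.684 | 0.532 | 0.448 (cut 16%) | 0.469 (cut 12%) |

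Middle row by hand. Visit 4 has variance 1 and covariance 0.584 with week 8. The mean of Visits 2 and 3 has variance (1 + 0.598)/2 = 0.799, covariance (0.584 + 0.631)/2 = 0.6075 with Visit 4, and (0.540 + 0.571)/2 = 0.5555 with week 8. R² = (0.584² × 0.799 − 2 × 0.584 × 0.5555 × 0.6075 + 0.5555²) / (0.799 − 0.6075²) = 0.435, leaving 0.565. Entering the three visits separately gives the same to three decimals, so averaging Visits 2 and 3 loses almost nothing.

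Holding the Visit 4 to week 8 correlation at these values and moving d from 0 to 0.7 moves the cut from 18-23% down to about 2-4%. With still less visit noise it tends to zero.

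**5. Correlation fading by a constant percentage per week.** Correlation R × φ^weeks, R from 0.5 to 0.8, mean of Visits 2 and 3 added:

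| Fading per week | SBP week 8 | FPG week 24 |
|---|---|---|
| 1% | 12-15% | 8-9% |
| 2% | 9-10% | 3-4% |
| 5% | 2-4% | under 1% |

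SBP gains more here only because its outcome lies 8 weeks from baseline and not 24.

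**6. Power illustration for SBP.** Assumed SD 14 mmHg, true difference 4 mmHg, 103 per arm, residual fractions from the middle row of step 4.
- Visit 4 only: SE = 14 × √0.659 × √(2/103) = 1.584; Φ(4/1.584 − 1.96) = 71%.
- With the second covariate: SE = 14 × √0.565 × √(2/103) = 1.466; Φ(4/1.466 − 1.96) = 78%.

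The variance ratio 0.659/0.565 = 1.17 is worth about 17% more patients for this test.

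**The case against.** The strongest reply is that nothing here is wrong. ANCOVA on treatment and one baseline is valid, standard and consistent with Section 11.1.1. That stands: this is unused efficiency, and it gives no reason to doubt the planned analysis.

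Other objections stand in part:
- **SBP is not a single reading.** The visit value averages three readings, so only between-visit variation can be reduced. The correlations above are between visit values, so the calculation already reflects this.
- **Antihypertensives may change in the lead-in.** Visit 2 SBP, and possibly Visit 3 SBP, can precede an adjustment in patients at or above 160/100 mmHg. This weakens the assumed correlations, Visit 2 most. It creates no bias, because everything precedes randomisation. Visit 3 alone is a defensible conservative choice, with a cut of about 6-12% under moderate assumptions.
- **The size rests on assumption.** It does. With rapid fading the gain is negligible; the cost is then one degree of freedom in about 206 patients.

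A reader might also infer that the primary test is weakened. The documents do not support that. HbA1c is powered at 90% as planned, and under assumed correlations typical of a stable measure (R 0.85-0.95, fading 1-3% per week) earlier values would cut its residual variance by only about 0-7%.

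**Conclusion.** The point holds as a low-cost improvement to two key secondary analyses. The direction is secure: usable pre-randomisation values are collected and no named model uses them. The size is not secure. Under assumed correlations the residual variance cut is about 3-24% for week-8 SBP, roughly 9-16% under moderate stability, and about 0-10% for week-24 FPG if correlation fades with time.

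Three stronger readings should be resisted. The plan contains no statistical error here, and the stated sample size is unaffected. It is not established that SBP gains most; that follows only if correlation fades with time. Nor does better SBP precision protect the testing sequence, since SBP is last; only the FPG gain can lower the risk of an early stop. The documents also do not show that either test is underpowered; they state no power for them.

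**What to change.** In Section 12.2.1, for FPG and SBP only, add a prespecified second covariate: the mean of the available Visit 2 and Visit 3 values that are not themselves serving as baseline. The qualification is needed because under Section 11.1.1 a missing Visit 4 value is replaced by an earlier one. Add a simple rule for patients with no such value, for example setting the covariate equal to baseline. For SBP, Visit 3 alone is acceptable if the sponsor prefers to avoid values taken before an antihypertensive adjustment.

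Keep baseline and change from baseline as defined in Section 11.1.1, so the quantity estimated does not change, and leave the primary HbA1c model as it is. The cost is a sentence or two in the protocol and SAP, settled before unblinding. It needs no new data, visits or patients.

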12.2.2 Analysis after the 28-week site- and patient-blinded extension period

All variables to be analyzed after the 24 weeks of double-blind treatment will be re-examined at the week 52 time point. In general, the data from this period will be summarized descriptively using point estimates and 95% confidence intervals. Details of the planned analyses will be provided in a separate Statistical Analysis Plan (SAP) specific to this period. The results from the extension period will be reported separately.

12.2.3 Analysis of safety

The safety evaluations will include analyses of AEs, laboratory values, ECG, vital signs (pulse and blood pressure), hypoglycaemic events, calculated creatinine clearance, estimated glomerular filtration rate and physical examination findings.

The analysis of safety will be based on the safety analysis set. Safety data gained during the 24-week double-blind treatment period, the 28-week site- and patient-blinded extension period as well as during the 3-week safety follow-up period will be evaluated. Safety data will be summarized descriptively and presented by treatment group. The primary safety analyses include all data regardless of rescue. For data such as hypoglycaemia, sensitivity analyses may be performed on data collected prior to rescue by replacing missing data using the LOCF approach.

